**Figure 4. Tricuspid Surgical Repair Techniques**

### 1.2.3 Transcatheter Methods of Treatment

Medical management is likely to provide only temporary symptom relief. The lack of sustained benefit from medical therapies and the low prevalence of surgery has prompted the search for alternative transcatheter repair and/or replacement therapies.

#### 1.2.3.1 Transcatheter Tricuspid Valve Replacement (TTVR)

Transcatheter valve replacement with the Edwards Sapien or Medtronic Melody valve has been described in the published literature on single case studies or limited retrospective clinical series, primarily for valve-in-valve patients or patients with rheumatic disease. In addition, the GATE Tricuspid Valved Stent (NaviGate Cardiac Structures, Lake Forest, CA) has been performed in patients under compassionate use and is under investigation.

#### 1.2.3.2 Transcatheter Tricuspid Valve Repair (TTVr)

In the past decade, transcatheter aortic valve replacement (TAVR) has been used successfully in increasing numbers and is considered a treatment option even in moderate risk patients. The success of TAVR stimulated attempts at transcatheter mitral valve replacement (TMVR) to facilitate percutaneous treatment of mitral regurgitation (MR). TMVR has been proven to be far more complex than TAVR. However, there are several transcatheter devices that are approved for transcatheter mitral valve repair (TMVr). The MitraClip System (Abbott Vascular, Santa Clara, CA) is approved for use in the EU (2008) and the U.S. (2013). The PASCAL System (Edwards Lifesciences) was recently approved in EU (2019) for treatment of mitral regurgitation. The Cardioband Mitral System (Edwards Lifesciences (formerly Valtech Cardio LTD, Or Yehuda, Israel) was also approved in the EU. TMVR devices are also being tested and the field of transcatheter repair and replacement of the mitral valve is expected to grow further in the following years. It is clear, therefore, that the next important step in the field of percutaneous treatment of structural heart disease will focus on the "forgotten", tricuspid valve.

Several transcatheter devices are being investigated for the treatment of TR. The devices that have been developed can be divided according to the therapeutic target as follows: annuloplasty/annular reconstruction devices, coaptation devices, and caval valve implantation (CAVI), and leaflet devices.

### ***Annuloplasty/Annular Reconstruction Devices***

The first commercially available transcatheter therapy for the treatment of TR was the Cardioband Tricuspid Valve Reconstruction System (Edwards Lifesciences, formerly Valtech Cardio LTD, Or Yehuda, Israel), which received CE mark in April 2018. Data from the TRI-REPAIR study showed that annular reduction provided significant reduction in EROA and was sustained at 6 months. Clinically and statistically significant improvements in functional status (NYHA Class and peripheral edema), quality of life (KCCQ Score) and exercise capacity (6MWD) were observed at 6 months.

Other annuloplasty devices including the Trialign System (Mitralign, Tewksbury, MA), the TriCinch System (4Tech Cardio Ltd., Galway, Ireland), TRAIPTA device (NIH, Bethesda, MD), Millipede IRIS Transcatheter Annuloplasty Ring (Millipede, Santa Rosa, CA), and MIA annuloplasty implant are in the investigational stage.

The Trialign System is a system that mimics the surgical Kay procedure, with the aim of reducing TR by bicuspidization obtained with the plication of the anterior and posterior annulus. Published 30-day follow-up results from the SCOUT trial (NCT02574650) showed that the Trialign device was safe, successfully reduced annular area and regurgitant orifice, and improved left ventricular forward stroke volume.

The TriCinch device is comprised of a corkscrew anchor that is anchored in the anteroposterior annulus and then retracted into the inferior vena cava by a Dacron band that connects the anchor to a self-expanding Nitinol stent. Data from the PREVENT trial (NCT02098200) showed an implant success rate of 75% (18/24) and four (17%) late anchor detachments during the 12-month follow-up period. A new generation of the device has been developed and is under evaluation in the PROTECT feasibility study (NCT03294200).

The TRAIPTA device is an experimental epicardial Nitinol loop placed around the atrioventricular groove providing an external annuloplasty. Currently, a new TRAIPTA device for human testing is under development.

The Millipede IRIS Transcatheter Annuloplasty Ring is a complete semi-rigid annuloplasty ring that is placed in the supra-annular position. It has been used for mitral valve repair and is under investigation.

The MIA is a device comprised of ultra-low mass proprietary compliant PolyCor™ anchors and MyoLast™ implantable elastomer that allow bicuspidization of the tricuspid valve. It is currently under investigation.

### ***Coaptation Devices***

The FORMA Tricuspid Transcatheter Repair System (Edwards Lifesciences, Irvine, CA) includes a Spacer that is placed in the center of the TV orifice improving leaflet coaptation, thereby aiming to reduce the large regurgitant orifice and decrease TR. One-year follow-up data on 18 patients treated in Canada and Switzerland under special access/compassionate use setting showed that use of the FORMA System was feasible and safe in high-risk patients with severe TR. In addition, follow-up data at 24-36 months showed considerable and sustained TR reduction accompanied by significant functional improvement. In the FORMA Early Feasibility Study (NCT02471807), significant TR reduction was observed and sustained at one year. Clinically significant and sustained improvements in NYHA functional class, 6MWD, and KCCQ scores at one year were observed, as well.

### ***Caval Valve Implantation***

Implantation of a prosthesis in the caval space has been performed as a last-resort approach for treatment with TR with refractory right HF as it aims to reduce the negative effects of venous congestion leading to reduced symptoms of right HF. While this does not directly correct the TR, it prevents back flow beyond the right atrium with the goal of reducing symptoms, normalizing liver function, and improving physical capacity. Lauten et al. reported the successful implantation of a self-expandable valve tailored to the dimensions of the inferior vena cava with significant reductions in IVC pressures. Similarly, the ongoing HOVER trial is assessing heterotopic implantation of the Edwards-Sapien XT valve in the inferior vena cava (NCT02339974). Of note, such an intervention may lead to ventricularization of the RV and cause severe deterioration in patients with severe RV heart failure.

### ***Leaflet Devices***

The MitraClip System (Abbott Vascular, Santa Clara, CA), which has been approved for mitral repair has also been used in the tricuspid valve. Edge-to-edge tricuspid valve repair with single or multiple clip(s) has been successfully used for the treatment of TR in selected high-risk patients with malcoaptation of the tricuspid valve. In a retrospective analysis of 42 cases treated at a single center in Germany, successful edge-to-edge repair was achieved in 83% (35/42) patients. In another report of 50 patients with right-sided HF and severe TR treated at 2 centers in Germany, persistent reduction of at least one TR grade was achieved in 90% of patients at 6 months and the NYHA class improved in 79% of patients. While several case reports and series

have been published on the use of the MitraClip System in the treatment of TR, it remains under investigation and is being evaluated in the TRILUMINATE study (NCT03227757).

The Edwards PASCAL System percutaneously delivers a leaflet reconstruction device, which brings the leaflets together around an intravalvular spacer using independently actuating clasps. Use of the PASCAL System in treating patients with mitral regurgitation has been shown to be safe and feasible with a high rate of technical success. Evaluation of the PASCAL System in treating patients with TR is warranted and clinical cases have been performed under a compassionate use setting (summarized in section 1.5).

**1.3 Intended Use of Device**

The Edwards PASCAL System is intended for patients with tricuspid regurgitation deemed to be potential candidates for transcatheter tricuspid valve repair with the PASCAL System by the local Heart Team.

**1.4 Prior Testing**

A Report of Priors contained in the Clinical Investigator’s Brochure (CIB) has been prepared for the PASCAL System. This document provides the prior testing conducted on the system components for pre-clinical testing, in-vivo testing, and biocompatibility testing.

**1.5 Prior Clinical Experience With the PASCAL System**

**1.5.1**

[REDACTED]

[REDACTED]

## 2 STUDY DEVICE

[REDACTED]

[REDACTED]

[REDACTED]

[REDACTED]

[REDACTED]

[REDACTED]

[REDACTED]

[REDACTED]

[REDACTED]

[REDACTED]

[REDACTED]

[REDACTED]

[REDACTED]

[REDACTED]

[REDACTED]

[REDACTED]

[REDACTED]

[figure not shown]
[REDACTED]

[REDACTED]

[REDACTED]

[REDACTED]

[REDACTED]

### 3 RISKS AND BENEFITS

The risks to patients receiving the PASCAL System procedure are listed in Section 3.1. The risks of participation are offset by the significant potential in clinical and functional benefits to patients with TR that comes through improving TV function.

#### 3.1 Potential Risks

Adverse events that are anticipated in this clinical study are believed to be consistent with those associated with other minimally invasive surgical and catheter-based interventional cardiac procedures. Complications may occur at any time during the procedure, post-procedure or follow-up period.

Anticipated or potential adverse events that may occur during the study are listed below. These events may be associated with the PASCAL System, transcatheter procedure, diagnostic cardiac tests (e.g. TEE, TTE, MSCT scan, exercise tolerance, etc.), ancillary procedures or may occur in the heart failure population over time. Complications associated with standard cardiac catheterization, the use of anesthesia and use of the PASCAL System could lead to the following outcomes: conversion to open heart surgery, emergent or non-emergent reoperation, explant, permanent disability, or death. There may also be other risks that are unknown at this time.

**The following anticipated adverse events have been identified as possible complications of the PASCAL System and procedure:**

- Abnormal lab values
- Allergic reaction to anesthetic, contrast, heparin, Nitinol
- Anemia or decreased Hgb, may require transfusion
- Aneurysm or pseudoaneurysm
- Angina or chest pain
- Anaphylactic shock
- Arrhythmias – atrial (i.e. AF, SVT)
- Arrhythmias – ventricular (i.e. VT, VF)
- Arterio-venous fistula
- Atrial septal injury requiring intervention
- Bleeding
- Cardiac arrest
- Cardiac failure
- Cardiac injury, including perforation
- Cardiac tamponade/pericardial effusion
- Cardiogenic shock
- Chordal entanglement or rupture that may require intervention
- Coagulopathy, coagulation disorder, bleeding diathesis
- Conduction system injury which may require permanent pacemaker
- Deep vein thrombosis (DVT)
- Deterioration of native valve (e.g. leaflet tearing, retraction, thickening)
- Dislodgement of previously deployed implant
- Dyspnea
- Edema

- Electrolyte imbalance
- Emboli/embolization including air, particulate, calcific material, or thrombus
- Endocarditis
- Esophageal irritation
- Esophageal perforation or stricture
- Exercise intolerance or weakness
- Fever
- Failure to retrieve any PASCAL system components
- Gastrointestinal bleeding or infarct
- Heart failure
- Hematoma
- Hemodynamic compromise
- Hemolysis
- Hemorrhage requiring transfusion or intervention
- Hypertension
- Hypotension
- Implant deterioration (wear, tear, fracture, or other)
- Implant embolization
- Implant malposition or failure to deliver to intended site
- Implant migration
- Implant thrombosis
- Infection
- Inflammation
- LVOT obstruction
- Mesenteric ischemia
- Multi-system organ failure
- Myocardial infarction
- Nausea and/or vomiting
- Nerve injury
- Neurological symptoms, including dyskinesia, without diagnosis of TIA or stroke
- Non-neurological thromboembolic events
- Pain

- Papillary muscle damage
- Paralysis
- PASCAL system component(s) embolization
- Peripheral ischemia
- Pleural effusion
- Pulmonary edema
- Pulmonary embolism
- Reaction to anti-platelet or anticoagulation agents
- Renal failure
- Renal insufficiency
- Respiratory compromise, respiratory failure, atelectasis, pneumonia - may require prolonged ventilation
- Retroperitoneal bleed
- Septal damage or perforation
- Septicemia, sepsis
- Skin burn, injury or tissue changes due to exposure to ionizing radiation
- Single leaflet device attachment (SLDA)
- Syncope
- Stroke
- Transient ischemic attack (TIA)
- Tricuspid valve injury
- Tricuspid valve stenosis
- Urinary tract infection and/or bleeding
- Vascular injury or trauma, including dissection or occlusion
- Valvular regurgitation
- Vessel spasm
- Ventricular wall damage or perforation
- Wound dehiscence, delayed or incomplete healing
- Worsening of heart failure
- Worsening tricuspid regurgitation / valvular insufficiency

There may be other risks that are unknown at this time. All safety events will be collected and reviewed throughout the entire study and follow-up period. The Investigators will be notified of any additional risks identified that could affect the health, safety or welfare of the study patients.

### **3.2 Minimization of Risks**

All efforts will be made to minimize the identified risks by taking the following measures:

- Selection of investigators in this study: Interventional Cardiologist – must be board certified (or equivalent), experienced with performing transcatheter heart valve repair and replacement, and skilled in percutaneous coronary interventions and structural heart interventions as well as access site management.
- Investigators will be trained in proper procedure performance and device operation prior to patient treatments. Training will include didactic and hands-on training with the PASCAL System.
- Well-defined clinical study protocol, including specific inclusion/exclusion criteria to enroll appropriate patients in the study.
- A Screening Committee ensures final eligibility of patients for participation in the study.
- There will be strong interdepartmental collaboration between interventional cardiology and cardiovascular surgery operators and a designated team of nurses, technicians and colleagues from supporting medical disciplines (e.g., anesthesiologist, heart failure specialist, echo-cardiographer, radiologist).
- The procedural location is to be an operating room, catheterization lab or hybrid operating room with fluoroscopic and echocardiographic imaging capabilities.
- Close patient monitoring during the implant procedure and follow-up period.
- Ongoing monitoring of study data and results, including the use of independent Clinical Events Committee (CEC) and Data Safety Monitoring Board (DSMB).

### **3.3 Potential Benefits**

The potential benefits associated with the use of the PASCAL System are related to eliminating the need for open chest surgery and cardiopulmonary bypass associated with surgical mitral repair/replacement by using a percutaneous approach. The potential benefits to patients are expected to be similar to those of other leaflet repair transcatheter devices. The benefits may include but are not limited to, the following:

- Delay in time to first surgical tricuspid valve replacement/repair and cardiopulmonary bypass
- Elimination of need for surgical tricuspid valve replacement/repair and cardiopulmonary bypass, thus reducing incidence of:
  - i. Reoperation due to cardiac complications
  - ii. Myocardial infarctions
  - iii. Neurological complications (i.e. TIA, stroke)
  - iv. Infections
  - v. Pulmonary complications (i.e. pulmonary edema) and the need for mechanical ventilation support required after the procedure
  - vi. Need for blood transfusions due to bleeding
  - vii. Post-procedural arrhythmias
  - viii. Pain and complications (i.e. deep wound infection) associated with sternotomy or thoracotomy
  - ix. Overall recovery time, including a reduction in the time spent in the intensive care unit
- The ability to reliably assess post-placement tricuspid regurgitation during the valve repair procedure (because the heart has not been arrested)
- Clinical improvement (e.g. NYHA Class, 6 minute walk test)
- Overall advancement of medical and scientific knowledge which may benefit future patients with similar conditions may be gained through this clinical study.
- There may also be other benefits that are unknown at this time

### 3.4 Justification For Clinical Study

This study, the first with the PASCAL System in the United States, is designed as a prospective, single arm, multi-center, early feasibility study. This study is designed to assess the safety and performance of the PASCAL System in the treatment of TR.

Treatments currently available for this patient population include medical therapy, surgical replacement or repair of the tricuspid valve, and alternative investigational transcatheter tricuspid valve repair systems (e.g. Edwards FORMA or Cardioband, Abbott MitraClip).

## 4 STUDY OBJECTIVES

The objectives of this early feasibility study are to:

- Evaluate the safety and performance of the PASCAL System
- Provide guidance for future clinical study designs utilizing the PASCAL System
- Provide guidance for future PASCAL System developments

Data collected in this clinical study will include safety and performance of the investigational system, as well as up to 5-year clinical outcomes.

## 5 FEASIBILITY ENDPOINTS

### 5.1 Safety Endpoint

Safety will be analyzed as a composite endpoint of Major Adverse Events (MAEs) at 30 days which includes:

- Cardiovascular mortality
- Myocardial infarction (MI)
- Stroke
- Renal complications requiring unplanned dialysis or renal replacement therapy
- Severe bleeding\*
- Unplanned or emergency re-intervention (either percutaneous or surgical) related to the device
- Major access site and vascular complications requiring intervention

### 5.2 Performance Endpoints

#### 5.2.1 Device Success

Device is deployed as intended and the delivery system is successfully retrieved as intended at the time of the patient's exit from the cardiac catheterization laboratory. *Per device analysis.*

---

\* Severe bleeding includes fatal, life-threatening, extensive, or major bleeding, as defined by MVARC [see also Appendix A: Study Definitions]

### 5.2.2 Procedural Success

Device success with evidence of a reduction in TR grade by at least one grade (scale: none/trace, mild, moderate, severe, massive, torrential\*9) at end of procedure, and without the need for a surgical or percutaneous intervention prior to hospital discharge. *Per patient analysis.*

### 5.2.3 Clinical Success

Procedural success without MAEs at 30 days. *Per patient analysis.*

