### **Death**

#### ***(MVARC Definition)***

All events with an outcome of death will be classified to determine whether the death was related to cardiovascular (CV) or non-cardiovascular (non-CV) cause.

Although categorizing the initiating or proximate cause of cardiovascular death may be difficult, major complications contributing to death should be identified. A diagnosis of non-cardiovascular death requires the primary cause to be clearly related to another condition (e.g., trauma, cancer, or suicide). For this study purpose, all deaths that are not unequivocally related to a non-cardiovascular condition are considered cardiovascular death.

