**B. Non cardiovascular Death**

Any death in which the primary cause of death is clearly related to another condition:

- Non cardiovascular infection and sepsis (e.g., pneumonia)
- Renal failure
- Liver failure
- Cancer
- Trauma
- Homicide
- Suicide
- Other noncardiovascular

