**Major Adverse Event (MAE)**

In this study, MAEs are defined as cardiovascular mortality, MI, stroke, renal complications requiring unplanned dialysis or renal replacement therapy, severe bleeding, unplanned or emergency re-intervention (either percutaneous or surgical) related to the device and major access site and vascular complications requiring intervention.

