3. STUDY ENDPOINTS

3.1 Safety Endpoint:

Safety will be analyzed as a composite endpoint of Major Adverse Events (MAEs) at 30 days which includes cardiovascular mortality, myocardial infarction (MI), stroke, renal complications requiring unplanned dialysis or renal replacement therapy, severe bleeding (includes fatal, life-threatening, extensive, or major bleeding, as defined by MVARC), unplanned or emergency re-intervention (either percutaneous or surgical) related to the device and major access site and vascular complications requiring intervention.

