3.2.3 Clinical Success

Procedural success without MAEs at 30 days. Per patient analysis.

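### Clinical success has no survival condition, so a patient who dies by day 30 of a clearly non-cardiovascular cause, with no MAE, still meets the written definition

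*Protocol*

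**What the plan says.** Clinical success is worded the same way in four places. Protocol 5.2.3 has "Procedural success without MAEs at 30 days"; the synopsis and Appendix A match it, and SAP 3.2.3 reads "Procedural success without MAEs at 30 days. Per patient analysis".

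The two parts of that definition are set out elsewhere:

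- **Procedural success** (Protocol 5.2.2) needs device success and a fall of at least one TR grade, judged "at end of procedure, and without the need for a surgical or percutaneous intervention prior to hospital discharge". It does not mention being alive.
- **MAE** is a closed list. Appendix A begins it "In this study, MAEs are defined as cardiovascular mortality, MI, stroke, renal complications requiring unplanned dialysis or renal replacement therapy, severe bleeding" and adds device-related re-intervention and major access-site or vascular complications needing intervention. Protocol 5.1 gives the mortality item as "Cardiovascular mortality", and SAP 3.1 agrees: "Safety will be analyzed as a composite endpoint of Major Adverse Events (MAEs) at 30 days which includes cardiovascular mortality, myocardial infarction (MI), stroke".

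Appendix A then divides deaths into two classes. Non-cardiovascular death is "Any death in which the primary cause of death is clearly related to another condition", with non-cardiovascular infection, renal failure, liver failure, cancer and trauma among the examples. The division leans towards the other class, because "all deaths that are not unequivocally related to a non-cardiovascular condition are considered cardiovascular death", and deaths of unknown cause are also adjudicated as cardiovascular.

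SAP 8.1 reports clinical success per patient for the ITT and as-treated cohorts and gives no rule for a patient who dies before day 30. SAP 6.1 generally takes patients without evaluable data out of percentage denominators.

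**The concern.** Restricting the safety composite to cardiovascular death is a defensible choice. It carries over less well into an endpoint called clinical success, where a non-cardiovascular death simply does not register. The result would be a patient reported as a clinical success at 30 days who was dead at 30 days.

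Such deaths are conceivable here. Protocol 3.1 lists sepsis, pneumonia, renal failure and multi-system organ failure among the possible complications, Protocol 8.8 calls for general anaesthesia, and Protocol 7.1 expects a mean age in the upper seventies. The mortality item turns on cause of death, not on relation to the device or procedure, so a procedure-related but clearly non-cardiovascular death would also fall outside it.

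At stake is the accuracy of one reported percentage in a small single-arm study that has guidance for later study designs as a stated objective (Protocol 4).

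**Working it through.** The plan gives no target rate or calculation for this endpoint that could be reproduced. The check is therefore a reading of the nested definitions, followed by simple proportions.

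**1. The definitions applied to one patient.** Suppose the device is deployed and the delivery system retrieved, TR falls by one grade, no intervention is needed before discharge, and the patient dies before day 30 of a cause adjudicated as unequivocally non-cardiovascular.

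| Condition | Source | Met? |
|---|---|---|
| Device success | Protocol 5.2.1 | Yes |
| TR reduction, no intervention before discharge | Protocol 5.2.2 | Yes |
| No cardiovascular death | Protocol 5.1; Appendix A | Yes, the death is in the other class |
| No MI, stroke, dialysis, severe bleeding, device re-intervention or major access complication | Protocol 5.1 | Yes, by supposition |
| Alive at 30 days | Not stated anywhere | Not required |

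Every written condition is met, so the definition returns success.

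**2. Deaths that do not pass through the gap.** Doubtful and unknown-cause deaths are cardiovascular by default. A renal death preceded by unplanned dialysis fails on the renal item. A fatal bleed fails on severe bleeding. What remains is unequivocally non-cardiovascular death in an otherwise successful, MAE-free patient.

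**3. Size per death.** Compared with scoring the death as a failure, the overstatement is 1/n.

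- n = 65 (Protocol 12.1, maximum enrolment): 1/65 = 1.5 points.
- n = 15 (SAP 2.2; SAP 1 ties the plan to protocol version A, whereas the protocol is now version C): 1/15 = 6.7 points.

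**4. Three possible scorings of one such death.** Assume, for illustration only, 52 successes in 65 as the definition is written.

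| Scoring of the death | Rate |
|---|---|
| Success (definition as written) | 52/65 = 80.0% (Clopper-Pearson 95% CI 68.2 to 88.9) |
| Removed from the denominator (one reading of SAP 6.1) | 51/64 = 79.7% |
| Failure | 51/65 = 78.5% (66.5 to 87.7) |

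Removing the patient still overstates the rate, by 79.7 − 78.5 = 1.2 points. For scale, the interval around 80.0% is 88.9 − 68.2 = 20.7 points wide.

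**5. Chance of its happening at all.** The documents give no rate for such deaths. With an assumed 30-day rate q of qualifying deaths, the chance of at least one is 1 − (1 − q)^n.

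- q = 0.5%: 28% at n = 65, 7% at n = 15.
- q = 3%: 86% at n = 65, 37% at n = 15.

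The range of q is an assumption, and the width of the result shows how little can be said about frequency.

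**The case against.** The strongest reply is that the gap is small and visible. Several parts of it stand:

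- The default rule in Appendix A closes most of the gap. Cardiovascular death is defined by contributing conditions, including heart failure with right ventricular dysfunction. A reader might infer that renal, hepatic or infectious deaths in right heart failure would routinely be scored as successes. The documents do not support that: where heart failure contributed, a death is hard to call unequivocally non-cardiovascular and would more likely be an MAE.
- The exclusions in Protocol 7.3 for low eGFR or chronic dialysis, marked frailty and life expectancy under 12 months should reduce such deaths further.
- Nothing is hidden. All-cause mortality is its own endpoint, with a 30-day Kaplan-Meier estimate and confidence interval in SAP 8.2.2, and all AEs and SAEs are listed for the ITT population.
- Analyses are descriptive (Protocol 12.3), and no visible decision rule uses clinical success. A reader might take it as the study's overall measure of net patient benefit, but the documents list it only as one of three performance endpoints.
- It is not certain that the patient would be counted as a success. The evaluable-data rule could be read as removing the patient, and the CEC Charter, which prevails over the protocol where they are inconsistent, is not among the documents.

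None of this puts a survival condition into the definition. Separate mortality reporting leaves the success percentage unchanged, and neither reading of the SAP scores the death as a failure. An unseen charter cannot be relied on to repair wording that the protocol and SAP state identically in four places.

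**Conclusion.** The point holds as a narrow wording gap. The definition allows clinical success for a patient who died by day 30 of an unequivocally non-cardiovascular cause without any MAE, and the SAP has no rule that overrides this.

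The per-death figures of 1.5 and 6.7 points assume analysis denominators of 65 and 15 respectively; a smaller denominator gives a larger effect. No total overstatement can be given, because the number of qualifying deaths is unknown and may be zero. No test, alpha or power is affected. Only the reported clinical success rate, and its use in planning later studies, would change.

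**What to change.** In Protocol 5.2.3, the synopsis, Appendix A and SAP 3.2.3, change the definition to: *Procedural success, alive and without MAEs at 30 days.*

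In SAP 8.1, add that death from any cause by day 30 counts as a clinical-success failure and stays in the denominator. The new definition alone would not settle this, because SAP 6.1 could still be read as removing the patient. Check that the CEC Charter agrees.

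Leave the MAE composite unchanged. The cost is two words in four places and one sentence in the SAP. No new data are needed, since deaths are already collected and classified. The clinical success rate may come out slightly lower.
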